#### 4 STUDY SCHEMA

Study Treatment: Bintrafusp alfa 1200mg IV Every 2 weeks until progression or unacceptable toxicity or maximum of 2 years.

##### 4.1 Informed Consent

The Investigator(s) (according to applicable regulatory requirements), or a person designated by the Investigator(s), and under the Investigator(s)'s responsibility, should fully inform the patient of all pertinent aspects of the clinical study including the written information giving approval/favorable opinion by the Ethics Committee (IRB/EC). All participants shall be informed to the fullest extent possible about the study, in language and terms they are able to understand.

Prior to a patients' participation in the clinical study, the written Informed Consent Form (Form B) and any other local applicable documents in accordance with local laws and regulations, should be signed, name filled in and personally dated by the patient or by the patient's legally acceptable representative, and by the person who conducted the informed consent discussion. A copy of the signed and dated written Informed Consent Form will be provided to the patient.

The Informed Consent Form used by the Investigator(s) for obtaining the patient's informed consent must be reviewed and approved by the appropriate Ethics Committee (IRB/EC) for approval/favorable opinion.

During a patient's participation in the trial, any updates to the consent form any updates to the written information will be provided to the patient.

Further information about the informed consent is available in Section 8.2 and Section 8.3.

## 4.2 Registration Guidelines

- All the patients must be registered with the Investigator(s) prior to initiation of treatment
- Forms A (registration) and B (consent) will be submitted
- The registration desk will confirm all eligibility criteria and obtain essential information (including patient number)

## 5 STUDY INTERVENTION

### 5.1 General Information of Study Intervention Bintrafusp alfa

Bintrafusp alfa is a first-in-class, bifunctional fusion protein comprised of the ECD of the human TGF- $\beta$ RII or TGF- $\beta$  Trap covalently linked to the C terminus of the heavy chain of the fully human IgG1, anti-PD L1 antibody via a flexible (Gly4Ser)4G linker.

### 5.2 Pharmaceutical Properties and Description of the Formulation

Bintrafusp alfa drug product is primarily provided as a sterile liquid formulation.

The Powder for Concentrate for Solution for Infusion (freeze-dried formulation) is packaged in United States Pharmacopeia (USP) and European Pharmacopeia (Ph. Eur.) type I glass vials. Each vial is filled with 45 mg of bintrafusp alfa (45 mg/vial) as a preservative-free powder containing histidine, trehalose dihydrate, sodium chloride, L-methionine, and polysorbate 20 (Tween 20). The vials are closed with a rubber stopper in lyophilization format complying with USP and Ph. Eur. and sealed with an aluminum plastic crimping cap. Only excipients that conform to the current USP and/or Ph. Eur. are used for bintrafusp alfa drug product.

The Concentrate for Solution for Infusion (liquid formulation) is packaged at a 10 mg/mL concentration in USP / Ph. Eur. type I 50R or 20R vials which are filled with drug product solution to allow an extractable volume of 60 mL (600 mg/60 mL) or 20 mL (200 mg/20 mL), respectively. The vials are closed with rubber stoppers with the same composition as used for freeze-dried formulation, but in serum format complying with USP and Ph. Eur. with an aluminum crimp seal closure.

The liquid formulation, compared with the freeze-dried formulation, has the same composition in terms of excipients, qualitatively and quantitatively, except for the addition of water. Of note, there is no change to the drug substance process.

The excipients are viewed as standard, and therefore, not a safety risk. The estimated volumes of delivery are anticipated to be either 250 or 500 mL, which are clinically acceptable.

### 5.3 Handling of the Dosage Form

For applications in clinical studies, the freeze-dried drug product must be reconstituted with 4.5 mL of water for injection and further diluted with 0.9% saline solution (sodium chloride injection)

supplied in an infusion bag. The liquid formulation is diluted directly with 0.9% saline solution. The estimated volumes of delivery are anticipated to be either 250 mL or 500 mL, which are clinically acceptable. Detailed information on infusion bags and medical devices to be used for the preparation of the dilutions and subsequent administration, and assigned dose levels and concrete volumes to be replaced to prepare the target doses are described in the Pharmacy Manual.

Bintrafusp alfa 1200mg will be administered intravenously on Day 1 of each 2-week study cycle. Bintrafusp alfa may be administered up to 3 days before or after the scheduled day of administration of each cycle due to administrative reasons.

#### **5.4 Instructions for Storage**

Bintrafusp alfa drug product must be stored at 2°C to 8°C until use. The storage condition is based on data from ongoing long-term stability studies with bintrafusp alfa.

Bintrafusp alfa drug product stored at room (23°C to 27°C) or higher temperatures for extended periods of time might be subject to degradation.

The liquid formulation is diluted directly with 0.9% saline solution. The chemical and physical in-use stability for the infusion solution of bintrafusp alfa in 0.9% saline solution has been demonstrated for a total of 72 hours at 2°C to 8°C and 24 hours at room temperature. However, from a microbiological point of view, the diluted solution should be used immediately and is not intended to be stored unless dilution has taken place in controlled and validated aseptic conditions. If not used immediately, in-use storage times and conditions prior to administration are the responsibility of the user. Do not freeze or shake the diluted solution.

No other drugs should be added to the infusion containers containing bintrafusp alfa.

#### **5.5 Bintrafusp Alfa Administration**

**Pre-medication:** Flat dose of 1200 mg administered over 60 minutes ( $\pm$  10-20 minutes) intravenous infusion once every 2 weeks. In order to mitigate infusion-related reactions, a premedication regimen of diphenhydramine 25 to 50 mg IV or oral equivalent and paracetamol 500 mg IV or oral equivalent is mandatory approximately 30 to 60 minutes prior to each dose of bintrafusp alfa.

**Setting:** bintrafusp alfa should be administered in a setting that allows for immediate access to an intensive care unit or equivalent environment and administration of therapy for anaphylaxis, such as the ability to implement immediate resuscitation measures. Steroids (dexamethasone 10 mg), epinephrine (1:1,000 dilution), allergy medications (IV antihistamines), bronchodilators, or equivalents, and oxygen should be available for immediate access.

**Observation period:** Following infusions, patients must be observed for 30 minutes post-infusion for potential infusion-related reactions.

Drug accountability and return, or local discard and destruction, if appropriate, must be completed with appropriate documentation for all study sites. Lot number, and expiry date for bintrafusp alfa is recorded in the study site as per local guidelines unless otherwise instructed by the Sponsor.

The Investigator is responsible for taking steps to maintain appropriate records and ensure appropriate supply, storage, handling, distribution and usage of study treatments in accordance with the protocol and any applicable laws and regulations.

## **5.6 Bintrafusp Alfa Adverse Event Management**

### **5.6.1 Bintrafusp Alfa Adverse Events**

Based on the available preclinical data, pharmacological class effect, and periodic safety reviews, the following were considered as adverse events upon Bintrafusp Alfa infusion and classified as:

- Important identified risks
  - Infusion-related reaction (IRR) including hypersensitivity (immediate): Signs and symptoms may include but are not limited to pyrexia, chills, flushing, hypotension, dyspnea, wheezing, back pain, abdominal pain, and urticarial
  - Immune-related adverse events (irAEs) including colitis, pneumonitis/interstitial lung disease, endocrinopathies (thyroid disorders including hyperthyroidism, hypothyroidism, autoimmune thyroiditis and adrenal insufficiency), Type I diabetes mellitus, renal disorders (acute renal injury), hepatitis (increased transaminase), retinal micro-vasculitis, myositis, skin reactions like rash (generalized, maculopapular, erythematous, pemphigoid)
  - Skin lesions with hyperkeratosis, keratoacanthoma, cutaneous squamous cell carcinoma possibly due to TGF- $\beta$  inhibition.
- Important potential risks
  - Treatment related anemia
  - Alterations in wound healing, repair of tissue damage, or mucosal bleeding events
  - Embryofetal toxicities
- Non-important potential risk:
  - Mucosal bleeding

Mucosal bleeding events are a potential risk for M7824. Respective risk mitigation measures have been implemented in the protocol.

The following side effects have been observed in  $\geq 10\%$  of patients among 630 patients treated with bintrafusp alfa according to the results from two oncology clinical studies in patients with advanced solid tumors. Common side effects (reported in more than 1 in 10 people) include:

- Anemia (low number of red blood cells)
- Decreased appetite
- Fatigue
- Pruritis (itching)

- Dyspnea (shortness of breath)
- Constipation (difficulty passing stools)
- Nausea (feeling sick to the stomach)
- Pyrexia (raised body temperature)
- Asthenia (decreased muscle strength)
- Diarrhea (frequent loose, watery stools)
- Abdominal pain
- Vomiting
- Cough
- Headache
- Epistaxis (bleeding from the nose)
- Rash (maculo-papular rash)
- Aspartate aminotransferase increased (elevation of liver enzyme)
- Oedema peripheral (buildup of fluid in the body causing swelling)

#### **5.6.2 Dose Modifications for Bintrafusp Alfa as Single Agent**

No dose reductions are permitted in this study, but doses may be omitted based on persisting toxicity. Any adverse event suspected to be immune-related should be managed according to the guidance for management of irAEs

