#### **5.6.3 Adverse Drug Reaction Requiring Bintrafusp Alfa Discontinuation or Delays**

The following adverse reactions (ADRs) require permanent treatment discontinuation of bintrafusp alfa:

**Any Grade 4 ADRs require bintrafusp alfa treatment discontinuation** except for single laboratory values out of normal range that are unlikely related to trial treatment as assessed by the Investigator(s), do not have any clinical correlate, and resolve within 7 days with adequate medical management.

**Any Grade 3 ADRs require bintrafusp alfa treatment discontinuation** except for any of the following:

- Transient ( $\leq$ 6 hours) Grade 3 flu-like symptoms or fever, which is controlled with medical management
- Transient ( $\leq$ 24 hours) Grade 3 fatigue, local reactions, headache, nausea, or emesis that resolves to Grade  $\leq$ 1
- Single laboratory values out of normal range (excluding Grade  $\geq$ 3 liver function test increase) that are unlikely related to trial treatment according to the Investigator(s), do not have any clinical correlate, and resolve to Grade  $\leq$ 1 within 7 days with adequate medical management
- Tumor flare phenomenon defined as local pain, irritation, or rash localized at sites of known or suspected tumor
- Change in Eastern Cooperative Oncology Group Performance Status (ECOG PS) to 3 that

resolve to  $\leq 2$  within 14 days (infusions should not be given on the following cycle, if the ECOG PS is 3 on the day of trial drug administration)

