***MANAGEMENT OF BLEEDING irAES IN PATIENTS TREATED WITH ICPis***

2.0 Bleeding Adverse Events	
Bleeding adverse events are considered important identified risk for bintrafusp alfa. In general, mild and moderate mucosal bleedings resolve without discontinuation of treatment. These events may include, but are not limited to the following:	
Epistaxis Hemoptysis Gingival bleeding Hematuria	
Mucosal/Non-tumor Bleeding	
Grading	Management
Grade 2	
If resolves to Grade <math>\leq 1</math> by the day before the next infusion, study intervention may be continued
 
If not resolved to Grade <math>\leq 1</math> by the day before the next infusion, but is manageable and /or not clinically relevant, consult Medical Monitor to assess if clinically reasonable to administer the following infusion.

Grade $\geq 3$	
Permanently discontinue treatment unless an alternative explanation can be identified (such as concomitant use of antithrombotic agents, traumatic events, etc.)
 
In case of alternative explanations, hold study treatment until the event recovers to Grade <math>\leq 1</math>
 
If Grade <math>\geq 3</math> bleeding event is observed, regardless of causality with the study intervention, upon resumption of study intervention bintrafusp alfa dose should be reduced by 50% (600 mg Q2W for participants dosed with 1200 mg, 1200 mg for participants dosed with 2400 mg). Once there is stable resolution and no recurrence of bleeding on reduced dose, Investigator is encouraged to communicate with Medical Monitor on potential dose re-escalation after careful benefit-risk assessment.

Grade 4	Treatment must be permanently discontinued if no alternative explanation is identified.
In case of rapid decrease of hemoglobin (Hgb), such as a decrease greater than 2.0 g/dL across a 2 weeks period, withhold the subsequent cycles of study intervention until Hgb is	

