stabilized and do a thorough assessment of bleeding (for example, upper and lower GI endoscopy, enhancement CT etc.); if Grade 1 or greater bleeding is observed or suspected, withhold the bintrafusp alfa until the bleeding is resolved/controlled and resume the dose of bintrafusp alfa reduced by 50%. Once Hgb decrease is recovered to  $\leq$  Grade 1 or baseline and stably controlled, the Investigator is encouraged to communicate with Medical Monitor to re-escalate the dose. The dose of bintrafusp alfa may be re-escalated to full dose once Hgb is stabilized without further need for blood transfusion in the subsequent cycles. The timing of re escalation may need a case-by-case decision. See Section Table 5 regarding stabilization of anemia.

Tumor Bleeding	
Grade $\geq$ 2	Study treatment must be held till the event recovers to Grade $\leq$ 1 Permanently discontinue treatment if the Investigator considers the participant to be at risk for additional severe bleeding.
Grade $\geq$ 3	If Grade $\geq$ 3 bleeding event had been observed, regardless of causality with the study intervention, upon resumption of the study intervention bintrafusp alfa dose should be reduced by 50%. Once there is stable resolution and no recurrence of bleeding on reduced dose, Investigator is encouraged to communicate with Medical Monitor potential dose re-escalation after careful benefit-risk assessment. Treatment should be permanently discontinued if the Investigator considers the participant to be at risk for additional severe bleeding. In case of rapid decrease of hemoglobin (Hgb), see Section Mucosal/Non-Tumor bleeding.

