### 5.6.7 Management of Treatment-Related Anemia

- Anemia is considered an important identified risk for bintrafusp alfa.
- Hematology assessment must be performed at baseline, prior to each bintrafusp alfa dose, at the end of treatment visit and at 28 ( $\pm 5$  days) days post-treatment safety follow-up.
- Participants must enter the study with Hgb values at least 9g/dl
- All relevant hematological testing for treatment-related anemias should be done prior to a blood transfusion, if clinically feasible

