### 5.6.8 Management of Bleeding Adverse Events

Bleeding Adverse Events	

 
● Bleeding adverse events are considered important identified risk for bintrafusp alfa.
 
● In general, mild and moderate mucosal bleedings resolve without discontinuation of treatment.
 
● These events may include, but are not limited to the following: 
 
○ Epistaxis
 
○ Hemoptysis
 
○ Gingival bleeding
 
○ Hematuria
 
 
 
	
Mucosal/Non-tumor Bleeding	
Grading	Management
Grade 2	
 
● If resolves to Grade <math>\leq 1</math> by the day before the next infusion, study intervention may be continued
 
● If not resolved to Grade <math>\leq 1</math> by the day before the next infusion, but is manageable and /or not clinically relevant, consult Medical Monitor to assess if clinically reasonable to administer the following infusion.
 

Grade $\geq 3$	
 
● Permanently discontinue treatment unless an alternative explanation can be identified (such as concomitant use of antithrombotic agents, traumatic events, etc.)
 
● In case of alternative explanations, hold study treatment until the event recovers to Grade <math>\leq 1</math>
 

	
 
• If Grade <math>\geq 3</math> bleeding event is observed, regardless of causality with the study intervention, upon resumption of study intervention bintrafusp alfa dose should be reduced by 50% (600 mg Q2W for participants dosed with 1200 mg, 1200 mg for participants dosed with 2400 mg). Once there is stable resolution and no recurrence of bleeding on reduced dose, Investigator is encouraged to communicate with Medical Monitor on potential dose re-escalation after careful benefit-risk assessment.
 

Grade 4	
 
• Treatment must be permanently discontinued if no alternative explanation is identified.
 

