
In case of rapid decrease of hemoglobin (Hgb), such as a decrease greater than 2.0 g/dL across a 2 weeks period, withhold the subsequent cycles of study intervention until Hgb is stabilized and do a thorough assessment of bleeding (for example, upper and lower GI endoscopy, enhancement CT etc.); if Grade 1 or greater bleeding is observed or suspected, withhold the bintrafusp alfa until the bleeding is resolved/controlled and resume the dose of bintrafusp alfa reduced by 50%. Once Hgb decrease is recovered to <math>\leq</math> Grade 1 or baseline and stably controlled, the Investigator is encouraged to communicate with Medical Monitor to re-escalate the dose. The dose of bintrafusp alfa may be re-escalated to full dose once Hgb is stabilized without further need for blood transfusion in the subsequent cycles. The timing of re escalation may need a case-by-case decision. See Section Table 5 regarding stabilization of anemia.
	
Tumor Bleeding	
Grade $\geq 2$	
 
• Study treatment must be held till the event recovers to Grade <math>\leq 1</math>
 
• Permanently discontinue treatment if the Investigator considers the participant to be at risk for additional severe bleeding.
 

Grade $\geq 3$	
 
• If Grade <math>\geq 3</math> bleeding event had been observed, regardless of causality with the study intervention, upon resumption of the study intervention bintrafusp alfa dose should be reduced by 50%. Once there is stable resolution and no recurrence of bleeding on reduced dose, Investigator is encouraged to communicate with Medical Monitor potential dose re-escalation after careful benefit-risk assessment. Treatment should be permanently discontinued if the Investigator considers the participant to be at risk for additional severe bleeding.
 
• In case of rapid decrease of hemoglobin (Hgb), see Section Mucosal/Non-Tumor bleeding.
 

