#### **6.6.6 Methods of Recording Adverse Events**

- All AEs must be documented in the appropriate section of the CRF. An SAE report form (initial or follow up) must be completed in case of any of the seriousness criteria is met.
- The following aspects must be recorded for each event in the CRF:
  - A description of the AE in medical terms, not as reported by the subject;
  - The date of onset (start date)
  - The time of onset (start time)
  - The date of recovery (stop date)
  - The time of recovery (stop time)
  - The severity of the sign and/or symptom or clinically significant abnormal laboratory
  - Value according to NCI-CTCAE v.4. If no toxicity grade is described for a given sign, symptom or abnormal laboratory value, the Investigator(s) will grade the severity as mid (grade 1), moderate (grade 2), severe (grade 3), or life-threatening or disabling (grade 4).
  - Death (grade 5) as defined by NCI-CTCAE v.4 is mainly regarded as an outcome and will be documented accordingly (see below).
- The causal relationship to binrafusp alfa as assessed by the Investigator(s); the decisive factor in the documentation is the temporal relation between the AE and the study drug. The following judgments of the causality to study drug or study procedures are to be used:
  - Not Related = not suspected to be reasonably related to the

investigational product. AE could not medically (pharmacologically/ clinically) be attributed to the investigational product under study in this protocol

- Related = suspected to be reasonably related to the investigational product. AE could medically (pharmacologically/ clinically) be attributed to the investigational product under study in this protocol
- Action taken on binrafusp alfa (none, medication discontinued, dose reduction, medication delayed, reduction of infusion rate).
- Other action (none, concomitant medication given, new or prolonged hospitalization, procedural surgery).
- The outcome according to the following definitions:
  - Recovered without sequelae (AE disappeared)
  - Recovered with sequelae (AE has resulted in permanent disability/incapacity)
  - Not yet recovered
  - Not recovered at death
  - Change in toxicity grade/severity or seriousness (e.g., an AE with no change of toxicity grade but newly classified as an SAE due to hospitalization.
  - Fatal (AE resulted in death)

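### Section 5.6.2 forbids the 50% dose reduction that the bleeding tables prescribe, and the entry haemoglobin limit is 8.0 g/dL in 3.1 but 9 g/dL in 5.6.7

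*Protocol*

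**What the plan says.** **Dose.** Section 5.6.2 states "No dose reductions are permitted in this study, but doses may be omitted based on persisting toxicity". Its second sentence sends events suspected to be immune-related to the irAE guidance.

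The bleeding rules are printed twice, once in the irAE tables of 5.6.5 and again in 5.6.8. After a Grade 3 or higher mucosal or non-tumour bleed, the first printing says that on resumption the "dose should be reduced by 50% (600 mg Q2W for participants dosed with 1200 mg, 1200 mg for participants dosed with 2400 mg"). For Grade 3 or higher tumour bleeding it says "upon resumption of the study intervention bintrafusp alfa dose should be reduced by 50" per cent. Section 5.6.8 repeats the mucosal rule: "upon resumption of study intervention bintrafusp alfa dose should be reduced by 50" per cent. For a haemoglobin fall of more than 2.0 g/dL over 2 weeks with Grade 1 or greater bleeding seen or suspected, the instruction is "withhold the bintrafusp alfa until the bleeding is resolved/controlled and resume the dose of bintrafusp alfa reduced by 50" per cent. Both printings allow later re-escalation in discussion with the Medical Monitor.

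Section 5.6.6's neighbour on case-report recording, 6.6.6, lists a dose reduction among the possible actions: "Action taken on binrafusp alfa (none, medication discontinued, dose reduction, medication delayed, reduction of infusion rate").

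**Entry haemoglobin.** Inclusion criterion 11c (3.1) sets a minimum of 8.0 g/dL. Section 5.6.7 says "Participants must enter the study with Hgb values at least 9g/dl".

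**The concern.** These are operative rules on how to dose and whom to enrol, and in each pair the two texts give different answers. They concern bleeding and anaemia, both of which 6.6.3 names as adverse events of special interest.

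On dose, the investigator who restarts at 1200 mg departs from the bleeding tables, and the one who restarts at 600 mg breaches 5.6.2. The same clinical situation could be handled in two ways, and either could be recorded as a protocol deviation.

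On entry, the registration desk confirms the eligibility criteria (4.2), and these are listed in section 3. The stricter limit sits in a toxicity-management section, where a check against that list would not find it.

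**Working it through.** No sample size, power or error rate is involved. The check is a comparison of the texts plus two small sums.

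**Step 1. Is the bleeding rule a dose reduction in the sense of 5.6.2?** The trial dose is a flat 1200 mg every 2 weeks (sections 4, 5.3 and 5.5). 50% of that is 0.5 × 1200 = 600 mg, the figure the tables print. This is a dose reduction, not an omitted dose.

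**Step 2. Does 5.6.2 apply to everyone?** Its heading refers to single-agent use, and the trial is a single-arm study of bintrafusp alfa alone (2.4 and 4). It therefore covers every patient.

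**Step 3. Can a patient reach the point where the rules collide?** Section 5.6.3 says "Any Grade 3 ADRs require bintrafusp alfa treatment discontinuation", with listed exceptions that do not include bleeding, and it also stops treatment for Grade 4 drug reactions with one laboratory exception. That removes many cases. Those that remain:

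| Event | May treatment resume? | Dose under the tables | Dose under 5.6.2 |
|---|---|---|---|
| Grade ≥3 mucosal bleed with another explanation | Yes, once Grade ≤1 | 600 mg | 1200 mg |
| Grade ≥3 tumour bleed, not a drug reaction, no further severe-bleeding risk seen by the investigator | Yes, once Grade ≤1 | 600 mg | 1200 mg |
| Haemoglobin fall >2.0 g/dL in 2 weeks with Grade 1 bleeding seen or suspected | Yes, once bleeding is controlled | 600 mg | 1200 mg |

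The third row is the easiest to reach, because Grade 1 bleeding triggers no discontinuation rule in 5.6.3.

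**Step 4. Does any text reconcile the two?** The cross-reference in 5.6.2 covers only events suspected to be immune-related. The tables apply the reduction after Grade 3 or higher bleeds whatever their cause, and 5.6.8 lies outside the irAE section. The dose-reduction option in 6.6.6 suggests that reductions were expected but gives no rule of precedence. The mention of participants on 2400 mg, a dose this trial does not use, suggests that the tables were carried over from elsewhere without adjusting 5.6.2. That is an inference.

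**Step 5. Entry haemoglobin.** The two limits differ by 9.0 − 8.0 = 1.0 g/dL. A patient from 8.0 to below 9.0 g/dL meets 11c and fails 5.6.7. For scale, the autoimmune haemolytic anaemia table in 5.6.5 puts Grade 3 at below 8.0 g/dL. The distance to that cut-off is 8.0 − 8.0 = 0 g/dL for a patient at the 11c limit and 9.0 − 8.0 = 1.0 g/dL at the 5.6.7 limit.

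**The case against.** The best case for leaving this alone has four parts.

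- **Section 5.6.2 is not absolute.** It defers to the irAE guidance, and the first bleeding table sits inside that guidance. This holds for bleeds suspected to be immune-related. It does not cover tumour bleeds or bleeds with another cause.
- **In practice the tables would be followed.** They are the only text on restarting after a bleed, both printings give the same rule, and this is a one-hospital trial. That makes inconsistent handling less likely, but a patient restarted at 600 mg would still be dosed against 5.6.2.
- **The reach is narrow.** Drug-related Grade 3 and 4 bleeds generally end treatment, and planned accrual is 38 patients. This is right, and it limits the weight of the point.
- **The haemoglobin texts can both be met, and the margin argument is thin.** A site enrolling only at 9 g/dL or above satisfies both, though nothing tells it to. The Grade 3 cut-off comes from a table for a different anaemia. Section 5.6.7 allows transfusion and growth factors, and 5.6.3 exempts certain isolated laboratory values. The 0 versus 1.0 g/dL comparison is therefore an illustration of scale, not a measure of risk. The disagreement over patients at 8.0 to below 9.0 g/dL remains.

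**Conclusion.** Both inconsistencies stand and should be fixed. The dose on resumption is either 1200 mg or 600 mg every 2 weeks, depending on which section is followed. The entry limit is either 8.0 or 9 g/dL.

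The number of patients affected cannot be derived from the protocol. Section 5.6.1 lists anaemia and epistaxis among side effects seen in at least 10% of 630 treated patients, but it gives no rate for the specific triggers or for haemoglobin at entry.

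No loss of efficacy at 600 mg is claimed, since the dose rationale in section 1 describes the exposure-efficacy effect in the randomised 500 mg versus 1200 mg data as relatively small. The response-rate decision rule (7.2) and the toxicity stopping rule (7.3) are not affected. The conclusion rests on reading the current text as it stands. Which rule was intended in each pair is not stated.

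**What to change.** 1. Amend 5.6.2 so that dose reductions are barred except for the 50% reduction, with possible re-escalation, that 5.6.5 and 5.6.8 set out after bleeding or a rapid haemoglobin fall. This keeps the safety measure and removes the conflict.
2. Delete the 2400 mg wording from both printings of the bleeding table.
3. Set criterion 11c to at least 9 g/dL to match 5.6.7. If 8.0 g/dL was intended, correct 5.6.7 instead. Either way the limit should appear in section 3, where eligibility is checked.

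The cost is a wording amendment. Adopting 9 g/dL narrows eligibility slightly, because patients from 8.0 to below 9.0 g/dL could no longer enter.
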